4.2. Per Protocol Analysis Set

The Per Protocol Analysis Set (PPAS) will be a subset of the FAS dataset. This set will exclude subjects based on the following criteria:

- Treatment compliance is outside the 80%-120% compliance range, calculated based on pill count (See [Section 6.5.3](#)).
- Subjects who did not have valid Baseline Hauser home diaries or fail to complete at least Week 5 Hauser diary measurements.
- Subject with any major protocol violations (including but not limited to the violation of entry criteria, use of excluded medication, errors in treatment assignment, loss to follow-up and missing data) that will impact data quality and/or the interpretation of the results.

A full list of protocol deviations will be compiled and reviewed to identify major and minor deviations, and the precise reasons for excluding subjects from the PPAS will be fully defined and documented (Subject Evaluability Determination List) before breaking the blind for the final database release.

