6.1.1.2. Sensitivity/Robustness Analyses

To support the interpretation of the primary analysis the following analyses will be performed:

Endpoint: Daily OFF time

- Analysis time points: Week 10 (End of Period A);
- Analysis populations (method of imputation for missing data): FAS, PPAS, FAS-Cohort 1 only, FAS-Cohort 2 only (See [Section 3.1](#));
- Analysis methodology: Change from baseline will be analyzed using the MMRM analysis (See [Section 5.2.2.1](#); FAS, FAS-Cohort 1 only), Bayesian ANOVA analysis (See [Section 5.2.2.3.1](#); FAS, FAS-Cohort 1 only), Dose Response analysis (See [Section 5.2.2.2](#); FAS, FAS-Cohort 2 only), and Bayesian Dose Response analysis (See [Section 5.2.2.3.2](#); PPAS, FAS-Cohort 2 only).

Reporting results:

- Raw data: The missing data pattern will be shown by treatment group and overall, for the Hauser Diary up to Week 10.
- Change from baseline: The point estimate, 90% confidence or credible interval for the point estimate, difference from placebo for each pair of treatment groups and the corresponding 90% confidence or credible interval will be presented. The MED estimate if applicable will be presented.

Figures

- Empirical cumulative distribution function showing % of subjects with change from baseline \leq cutoff value at Week 10 by treatment group; (any drop outs are assigned to the left side of x axis).

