6.5.3. Study Treatment Exposure

Duration of exposure will be presented in tables and listings in accordance with the Pfizer Data Standards.

Compliance will be calculated and summarized across the whole double-blind treatment phase, and by visit. Compliance will be based on the dosing record, and calculated as:

$$\% \text{Compliance} = 100 \times (\text{Actual \# of Capsules Taken}) / (\text{Total \# Capsules Prescribed})$$

Subjects who fail to return blister information will be considered missing for that visit.

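### Per-protocol membership for the Week 10 endpoint can be changed by dosing after Week 10, because SAP 4.2 sets no cut-off at the endpoint

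*SAP*

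**What the plan says.** SAP Section 6 uses the PPAS for the primary endpoint only, with the Full Analysis Set (FAS) as primary. SAP Section 6.1.1.2 and Appendix 1 give the PPAS one run, the "Bayesian Dose Response analysis" of Week 10 OFF time.

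SAP Section 4.2 has three exclusion criteria:

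- Compliance: "Treatment compliance is outside the 80%-120% compliance range, calculated based on pill count", with a reference to Section 6.5.3.
- Diaries: "Subjects who did not have valid Baseline Hauser home diaries or fail to complete at least Week 5 Hauser diary measurements".
- Major protocol violations, with examples that include "loss to follow-up and missing data) that will impact data quality and/or the interpretation of the results".

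On compliance, Section 6.5.3 says: "Compliance will be calculated and summarized across the whole double-blind treatment phase, and by visit". The formula is units taken over units prescribed. The section adds: "Subjects who fail to return blister information will be considered missing for that visit". It does not say which figure decides PPAS membership, or whether units still count as prescribed after a subject stops.

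Section 4.2 also provides for a review before the blind is broken, in which "the precise reasons for excluding subjects from the PPAS will be fully defined and documented".

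In the protocol, the endpoint falls at Day 70 (Section 2.4.1) and dosing runs from Day 1 to Day 105 (Section 6.2.2). Section 5.3 makes dosing outside 80%-120% a protocol deviation. The visit lists in Section 6.2 apply the same range at every scheduled visit, including Day 91 and Day 105. Protocol Section 9.2 describes the per-protocol set with a lower limit of 80% only, also with no time window.

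**The concern.** A per-protocol run of a Week 10 endpoint would normally be restricted by conduct up to Week 10. Here 35 of the 105 dosing days, one third, fall after the outcome has been recorded, and no criterion in Section 4.2 is closed at that point. Two kinds of misclassification are possible. A subject who dosed fully until the endpoint may be dropped for what happened afterwards. A subject who was under-dosed before the endpoint may be kept because of good dosing afterwards.

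The first kind matters because stopping or skipping tablets in Period B may plausibly depend on tolerability or perceived benefit, and so on dose. Selecting subjects on events after the outcome could then distort the dose comparison that the run is meant to check.

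The open window also sits oddly with SAP Section 6. For subjects not consented under Amendment 2 before Period B, Section 6 confines efficacy data to the period through Week 10, yet their Period B dosing could still decide whether their Week 10 result enters the PPAS.

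**Working it through.** The documents give no figure for PPAS size or for expected compliance, so there is none to reproduce on this point. The sample-size figures in Protocol Section 9.1 do not depend on it.

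**Inputs.** Endpoint at Day 70; last dose at Day 105; so 70 dosing days to the endpoint and 105 - 70 = 35 in Period B. Limits are 80% and 120%. Three tablets are taken each day (Protocol Section 5.5), so percentages are the same in days or tablets. Assumption for the whole-phase figure: all 105 days count as prescribed.

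**1. Exclusion on the whole-phase figure.**
- Doses needed: 0.80 × 105 = 84.
- With 70 of 70 taken to Day 70, Period B must supply 84 - 70 = 14 of 35 (40%). Fewer than 14 excludes.
- 10 of 35 in Period B: (70 + 10)/105 = 80/105 = 76%, excluded.
- None in Period B: 70/105 = 66.7%, excluded. Moving the Day 70 and Day 105 visits within their ±3-day windows gives 67/108 = 62% to 73/102 = 72%, still excluded.

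**2. Exclusion on the by-visit figures, if any failing visit excludes.**
- Days 71-91 hold 21 doses and Days 92-105 hold 14. The 80% limits are 0.80 × 21 = 16.8 and 0.80 × 14 = 11.2.
- Ten doses in Period B cannot reach either limit, however they are spread, so both visits fail and the subject is excluded.
- This reading is stricter on Period B than the whole-phase one: falling below 80% at one visit is enough, whereas the whole-phase figure tolerates down to 40% in Period B after full earlier dosing.

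**3. Retention on the whole-phase figure.**
- With 35 of 35 in Period B, the subject needs 84 - 35 = 49 of 70 before Week 10: 49/70 = 70%. The visit windows move this to between 68% and 72%.
- With Period B at the 120% limit: 1.2 × 35 = 42, and (84 - 42)/70 = 60%.
- With full dosing except in Period A (Days 36-70), that period alone can fall to (84 - 70)/35 = 40%.

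**4. Retention on the by-visit figures.** A failing visit before Week 10 excludes whatever follows, so later dosing cannot compensate.

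**5. With the count ended at Day 70.** Full dosing to Day 70 and none after scores 70/70 = 100% and is kept. The subject with 49 of 70 scores 70% and is excluded, even with full Period B dosing.

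**The case against.** The strongest reply is that Section 4.2 is not the final word. Deviations are graded and exclusions documented before unblinding, and that review could choose a sensible window. It could, but it is given none to apply, and the only compliance definition it is pointed to runs to Day 105.

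Several stronger readings are tempting, and the documents do not support them:

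- *That events after Week 10 decide membership.* They can alter it. The Baseline and Week 5 diary rule, entry-criteria violations and assignment errors are settled before the endpoint.
- *That a subject lost in Period B is removed.* The criterion is confined to major violations that affect data quality or interpretation. Loss at Week 12 after a complete Week 10 diary has no obvious effect on a Week 10 result. Unreturned blister information makes that visit's compliance missing, not zero. What remains is that the criterion has no time limit.
- *That good Period B dosing generally hides poor earlier dosing.* This needs the whole-phase figure, which the SAP does not name as the one that counts. With Period B at 100% it is confined to 70%-80% compliance before Week 10. Under-dosing at an earlier visit is recorded as a deviation under the protocol and could still be graded major.
- *That a subject who stops in Period B must fail.* If the prescribed count ends at discontinuation, compliance could remain at 100%. The documents leave this open.

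It is also fair that the examples are single subjects. The documents give no Period B adherence by arm, so neither the number reclassified nor the direction of any bias can be estimated.

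**Conclusion.** The point holds in limited form. No PPAS criterion is closed at Week 10, and on both compliance figures in Section 6.5.3 poor Period B dosing can exclude a subject with full dosing to Day 70 and a valid Week 10 diary. The 76% example assumes that all 105 days count as prescribed; the by-visit example assumes that any failing visit excludes. Retention of a subject with 70%-80% compliance before Week 10 arises only if the whole-phase figure decides, and by-visit deviations may still catch it.

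The consequence is confined to one sensitivity run. A reader might infer that the primary result is at risk or that the PPAS run is worthless; neither follows. The FAS analysis does not use these criteria, and how far the PPAS estimate would move is unknown. The rule should still be settled before unblinding, since it lets conduct after the outcome decide who is analysed.

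**What to change.** In SAP Section 4.2:

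1. Define PPAS compliance as tablets taken divided by tablets prescribed from Day 1 to the Week 10 visit, or to the last dose if earlier, and state how the denominator is counted after a subject stops.
2. Count loss to follow-up, missing data and other deviations arising during treatment only if they occur up to the last Week 10 diary day. Entry-criteria violations and assignment errors stay as they are.

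In SAP Section 6.5.3, keep whole-phase compliance as a descriptive summary. Reconcile the data source, which is a pill count in Section 4.2 and the dosing record in Section 6.5.3.

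The cost is a few sentences before unblinding. Accountability is already done at the Day 70 visit (Protocol Section 6.2.10), so no data collection or treatment rule changes.

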4.3. Safety Analysis Set

The safety analysis set will include all patients who received at least one dose of PF-06649751 or placebo. The safety analysis set is the primary population for treatment administration/compliance and safety.

All subjects who receive at least one dose of study medication will be classified according to the actual study treatment received. A randomized but not treated subject will be excluded from the safety analyses. A treated but not randomized subject or a randomized but took incorrect treatment subject will be reported under the treatment actually received.

CCI

5. GENERAL METHODOLOGY AND CONVENTIONS

See the Interim Analysis Plan (IAP) and Internal Review Committee (IRC) Charter for details on any unblinding for the interim analysis.

The blind for the study will be broken and the final analysis of the study data will be conducted once the last remaining subject has completed the study or is withdrawn from the study prior to completion, all data have been entered into the database, all data issues resolved, the Per Protocol Analysis Set (PPAS) has been determined, and the database has been locked.

CCI

5.1. Hypotheses and Decision Rules

5.1.1. Statistical Hypotheses

There are no formal statistical hypotheses in this study generally, and the study decision will be based on the two-part decision rule described in [Section 5.1.2](#) on the primary endpoint daily OFF time in hours at Week 10. To control its overall study Type I error, a preliminary dose-response trend test of the hypothesis of H_0 : no effect for all doses will be performed at the one-sided 0.05 level.

5.1.2. Statistical Decision Rules

The decision criteria for efficacy are given as below, which will be based on a Bayesian interpretation of the results:

- C1: Point estimate of PF-06649751 vs. placebo effect ≥ 1.5 hours, and
- C2: 95% confident of PF-06649751 vs. placebo effect ≥ 0 .

Better is defined as a reduction in the daily OFF time.

No adjustments for the interim analysis or multiple comparisons will be made.

5.2. General Methods

Descriptive summaries for the efficacy, safety, baseline, and CCI will be displayed overall (combining both cohorts) and by cohort/treatment using the following combinations.

- Overall
 - Placebo;
 - PF-06649751 1 mg QD;
 - PF-06649751 3 mg QD;
 - PF-06649751 7 mg QD;
 - PF-06649751 15 mg QD; all 15 mg QD subjects;
 - PF-06649751 15-15 mg QD (safety only); subjects not requiring down titration;
 - PF-06649751 15-7 mg QD (safety only); subjects requiring down titration.
- Cohort 1
 - Placebo
 - PF-06649751 15 mg QD;
 - PF-06649751 15-15 mg QD (safety only);
 - PF-06649751 15-7 mg QD (safety only).
- Cohort 2
 - Placebo;
 - PF-06649751 1 mg QD;
 - PF-06649751 3 mg QD;
 - PF-06649751 7 mg QD;
 - PF-06649751 15 mg QD;
 - PF-06649751 15-15 mg QD (safety only);
 - PF-06649751 15-7 mg QD (safety only).

Note that several visits have been changed as a result of the B7601003 Protocol Amendment 2. Days 14 (Week 2) and 21 (Week 3) were required “in-clinic” visits and now may be handled as phone visits, so those with phone visits will have less data collected. Additionally, Day 91 (Week 13) is now exclusively a phone visit, so only subjects consented under Protocol Amendment 2 will have data available. All available visit data will be reported, and for descriptive statistics by time point each visit will be represented. Additionally, for subjects randomized in Japan, specific “in-clinic” visits (eg, Days 15 and 22) were not previously mentioned in the previous version of the SAP, but will be included in all reporting. Tables and listings will add footnotes as appropriate.

5.2.1. Analyses for Binary Data

Analyses for any binary data output will show the number and percentage of subjects in each response category, and the response rate and its 90% confidence interval (CI) will be calculated. The confidence interval of the response rate will be calculated based on a normal approximation method. Also, the difference of the response rates (with 90% CIs) between each PF-06649751 treatment group and placebo group will be presented.

The analyses for binary data will utilize the logistic regression model (SAS code will be provided in the Programmer's Analysis & Reporting documentation). The response variable of the model will be the binary measurement (CCI [REDACTED]). The model will include the following terms as explanatory variables: geographic region and treatment. The odds ratio and its 90% confidence interval comparing each PF-06649751 dose versus placebo will be presented.

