#### **9.1. Sample Size Determination**

The sample size is based on a pair-wise comparison of a dose of the PF-06649751 against placebo and is based on the primary endpoint, the change from Baseline to Week 10 (end of Period A) in the daily OFF time. The decision criteria for efficacy are given as below, which will be based on a Bayesian interpretation of the results:

- C1: Point estimate of PF-06649751 vs. placebo effect  $\geq 1.5$  hours, and
- C2: 95% confident of PF-06649751 vs. placebo effect  $\geq 0$ .

Better is defined as a reduction in the daily OFF time.

The sample size indicates that 32 evaluable subjects per arm will give sufficient precision for a comparison of an active dose versus placebo to meet criterion C2 with observed effects of  $\geq 1.5$  hours (Criterion C1). It's estimated that the probability of passing both criteria for a true effect of 2.25 hours would be 85%, and the probability of passing the criteria for a true null effect (0 hour) would be 2%.

Accounting for a 10% rate of non-evaluable subjects as well as dropouts before the stable dose period (ie, by 5 weeks post dose), 36 subjects per arm and an approximate total of

198 subjects (54 in Cohort 1 and 144 in Cohort 2) are expected to be randomized for the study. Depending on actual enrollment, additional subjects may be randomized in the same treatment ratio, but there will be no more than 260 subjects in total.

The calculations were based on an estimate of the variability obtained from a meta-analysis of the historical Parkinson's disease trials. This provided an estimate of the between subject standard deviation of 2.9 hours in change from baseline in daily OFF time. The meta-analysis also provided an informative prior for placebo effect, which will be included in the Bayesian data analysis.

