2.2. Study Design

The study has a randomized, double-blind, placebo-controlled parallel group design. Approximately 198 subjects from approximately 60 centers in approximately 6 countries will be randomized to 5 treatment groups (15 mg QD, 7 mg QD, 3 mg QD, 1 mg QD, or placebo), initially in a 2:0:0:0:1 ratio of approximately 54 subjects (Cohort 1) followed by a 1:2:2:2:1 ratio of approximately 144 subjects (Cohort 2), using a central randomization system with randomization blocks stratified by region. Geographic region will be defined as North America, Japan, and Europe.

[figure not shown]
Each subject will participate in the study for approximately 25 weeks including up to a 45 day screening period, 15 week double-blind treatment period (comprising up to a 3 week titration, 2 week dose adjustment, 5 weeks of primary efficacy with adjunctive treatment to stable L-Dopa (Period A), and 5 weeks of maintenance with adjunctive treatment to stable L-Dopa (Period B)), and an approximately 28 day follow-up period.

Note that prior to B7601003 Protocol Amendment 2 Days 14 and 21 were required in-clinic visits, but now with the option to be phone visits, as applicable. The impact of this change will be noted in subsequent sections.

For sites in Japan, the Week 2 (Day 14) and Week 3 (Day 21) visits during the Titration Period must be conducted as site (in-clinic) visits. Additionally, two additional phone visits are required a day after both the Day 0 (Randomization) Visit (Day 1) and Week 1 Visit (Day 7 [+3 day window]) and two additional study site visits are required a day after both Week 2 Visit (Day 14 [+3 day window]) and Week 3 Visit (21 [+3 day window]), ie Day 15 and Day 22 respectfully. Phone visits can optionally be conducted as site visits (eg, for logistical reasons).

The study design is illustrated in the figure below.

Figure 1. Study Schematic

Each subject is planned to be up-titrated in a double-blind fashion to the assigned target dose level of PF-06649751 or placebo according to the following titration scheme:

Table 2. Proposed Titration Schemes for PF-06649751 and Placebo Doses

Week/ Start Day of Dose Level	Treatment Group				
	Placebo	1 mg	3 mg	7 mg	15 mg
Week 1 / from Day 1	P	1 mg	1 mg	1 mg	1 mg
Week 2/ from Day 8	P	1 mg	3 mg	3 mg	3 mg
Week 3 / from Day 15	P	1 mg	3 mg	7 mg	7 mg
Weeks 4-15 / from Day 22	P	1 mg	3 mg	7 mg	15 mg

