6.6.1. Adverse Events

Adverse events will be listed and summarized within treatment group in accordance with the Pfizer Data Standards.

The details of Tier-1, Tier-2 and Tier-3 AEs are described in [Section 3.5.1](#).

Adverse events within Tier-1 and -2 will be summarized using Risk Differences between each PF-06649751 group and placebo, together with 95% CI. A graphical presentation of the percentage of subjects with each AE and Risk Difference (with 95% CI) ordered by decreasing risk difference will be shown for the Tier-1 and -2 AEs separately. Significance tests will be performed for the Tier-1 adverse events. There will be no multiplicity adjustment for these significance tests.

For Tier-1 and Tier-2 adverse event outputs, the following footnotes will be used: “P-values and confidence intervals are not adjusted for multiplicity and should be used for screening purpose only. The 95% Confidence intervals are provided to help gauge the precision of the estimates for Risk Difference. Risk Difference is computed as PF-06649751 1 mg versus Placebo, PF-06649751 3 mg versus Placebo, PF-06649751 7 mg versus Placebo, and PF-06649751 15 mg versus Placebo.”

Tier-1 events for risk difference and relative risk will use unconditional exact methods (an approach proposed by Chan and Zhang, 1999⁶) based on standardized statistics. For Tier-2 events, an asymptotic approach will be performed.

The Tier-3 adverse events will be described as part of the overall AE summary.

It should be recognized that most studies are not designed to reliably demonstrate a causal relationship between the use of a pharmaceutical product and an adverse event or a group of adverse events. Except for select events in unique situations, studies do not employ formal adjudication procedures for the purpose of event classification. As such, safety analysis is generally considered as an exploratory analysis and its purpose is to generate hypotheses for further investigation. The 3-tier approach facilitates this exploratory analysis.

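### SAP 5.2.1 sets an unnamed normal-approximation 90% CI for binary response rates in arms of 18 to 54; if that is Wald, it under-covers at low or high rates and is 0%-0% with no responders

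*SAP*

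**What the plan says.** SAP 5.2.1 covers all binary outputs: "Analyses for any binary data output will show the number and percentage of subjects in each response category". Every such rate also gets an interval at the 90% level. One sentence fixes how it is obtained: "The confidence interval of the response rate will be calculated based on a normal approximation method". The visible text gives no variant, no small-sample alternative and no rule for zero counts. The section also asks for 90% CIs on the difference in rates from placebo, without naming a method. For the comparison itself, "The analyses for binary data will utilize the logistic regression model", with region and treatment as terms and an odds ratio with a 90% CI for each dose.

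SAP 5.2 requires descriptive summaries to be "displayed overall (combining both cohorts) and by cohort/treatment using the following combinations". SAP 2.2 gives the cohort sizes and allocation ratios that determine the arm sizes. The binary measurement itself is blacked out, and no expected response rate is visible in either document.

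**The concern.** The ordinary reading of a normal-approximation interval for one proportion is the Wald interval. It estimates its own standard error from the observed rate. That standard error is too small when few subjects respond, or nearly all do, and it is zero when none or all do. In arms of 18 to 54 this matters if the redacted endpoints have low or high rates: the table would then show a response rate as better known than it is. The effect is largest in the by-cohort displays, where placebo has about 18 subjects in each cohort and 15 mg has about 18 in Cohort 2.

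**Working it through.** **The plan's own figure.** The only design calculation concerns the continuous primary endpoint (protocol 9.1). With SD 2.9 h and 32 evaluable subjects per arm, SE = 2.9 × √(2/32) = 0.725 h. Criterion C2 is met once the estimate reaches 1.645 × 0.725 = 1.19 h, so C1 (1.5 h) governs. P(pass | 2.25 h) = Φ(0.75/0.725) = 0.850 and P(pass | 0 h) = 1 − Φ(1.5/0.725) = 0.019. These match the stated 85% and 2%. Allowing for 10% loss, 32/0.9 gives 36. No such calculation exists for any binary endpoint.

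**Arm sizes (SAP 2.2).**
- Cohort 1: 54 subjects at 2:1 gives 36 on 15 mg and 18 on placebo.
- Cohort 2: 144 subjects at 1:2:2:2:1 gives 144/8 = 18 per unit. That is 18 on 15 mg, 36 on each of 7, 3 and 1 mg, and 18 on placebo.
- Pooled: 36 + 18 = 54 on 15 mg, 18 + 18 = 36 on placebo, and 36 in every other arm.

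The planned 10% loss would make evaluable arms slightly smaller and the shortfall slightly larger.

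**Formulas**, for x responders of n, p = x/n, z = 1.645 (two-sided 90%, an assumption):
- Wald: p ± z√(p(1−p)/n).
- Wilson: [p + z²/2n ± z√(p(1−p)/n + z²/4n²)] / (1 + z²/n).
- Exact coverage at true rate π: the sum of binomial(n, π) probabilities over every x whose interval contains π.

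**One case in full.** Take n=36 and π=3%. The Wald intervals that contain 3% are those for x = 1 to 4. Coverage = 0.372 + 0.201 + 0.071 + 0.018 = 0.662. Nearly all the loss comes from x = 0, which has probability 0.97³⁶ = 0.334 and an interval of 0%-0%. At n=18 the same sum runs over x = 1 to 3: 0.322 + 0.085 + 0.014 = 0.42.

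**Wald coverage of the nominal 90% interval:**

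| True rate | n=18 | n=36 | n=54 |
|---|---|---|---|
| 2% | 30.0% | 51.1% | 66.0% |
| 5% | 59.2% | 83.4% | 74.2% |
| 10% | 82.2% | 86.4% | 90.0% |
| 20% | 88.5% | 83.1% | 90.4% |
| 30% | 88.0% | 89.9% | 88.9% |
| 50% | 90.4% | 86.8% | 86.6% |
| Mean, 3-20% | 77% | 85% | 87% |
| Mean, 20-80% | 86.9% | 88.3% | 89.0% |

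Coverage is a sawtooth in the true rate: at n=36 it is 91.5% at 7% and 77.2% at 8%. The means are therefore a fairer summary than single rates. Coverage at π and 1−π is the same, so the 3-20% row also applies to 80-97%.

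**Wilson for comparison.** Mean coverage over 3-97% is 90-91% at n=18 and about 90% at n=36. It also oscillates, with minima of 83.6% at n=18 and 85.9% at n=36.

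**No responders.** Wald gives 0%-0% at every n. The Wilson upper limit is z²/(n + z²):
- n=18: 2.706/20.706 = 13.1%
- n=36: 2.706/38.706 = 7.0%
- n=54: 2.706/56.706 = 4.8%

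At a true rate of 5% the chance of seeing no responders is 0.95ⁿ: 39.7%, 15.8% and 6.3% respectively.

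**The case against.** Much of the other side stands.

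- **Wald is not named.** A score interval also rests on a normal approximation and has neither defect. The Wald results are conditional on that reading, although it is the usual one.
- **Relevance cannot be shown.** The binary endpoints and their rates are redacted, and every visible primary and secondary efficacy endpoint is continuous. If the rates lie between 20% and 80%, the pooled arms lose only one to two points of coverage on average.
- **Nothing decisive depends on it.** The single-arm interval is descriptive. It enters neither C1/C2 (SAP 5.1.2), nor the primary analysis (SAP 6.1.1.1), nor the odds ratios. Arms of 18 occur only in by-cohort displays.

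A reader might also infer that the SAP contradicts itself, because "Tier-1 events for risk difference and relative risk will use unconditional exact methods". The documents do not support that. SAP 3.5.1 defines Tier-1 by clinical importance, not by rarity, and says none had been defined. The exact method there is for comparisons between arms, not for a single-arm rate, and SAP 6.6.1 assigns Tier-2 events an asymptotic approach.

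What these objections do not remove is that the plan states a method whose ordinary reading breaks down at zero counts and performs poorly near 0% and 100%, when a better one costs almost nothing.

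**Conclusion.** The point holds as a minor improvement. Under the Wald reading, the nominal 90% interval averages 77%, 85% and 87% coverage at n = 18, 36 and 54 for true rates of 3-20%, and it collapses to zero width with no responders. A reader might infer that the interval falls well short of 90% whatever the rate, or that this trial's printed intervals will be wrong. The documents support neither: mid-range rates in the pooled arms average 88-89%, and the actual rates are not visible. The conclusion rests on three assumptions: Wald is meant, the interval is two-sided, and enrolment follows the planned arm sizes. No efficacy decision changes.

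**What to change.** Replace the sentence on the interval method in SAP 5.2.1 with: *The 90% CI of each response rate will be the Wilson score interval.* If Wilson was already intended, this only makes the text explicit. An exact (Clopper-Pearson) interval would also remove the zero-width result, but it is conservative: mean coverage over 2-98% is 95.0%, 93.8% and 93.2% at n = 18, 36 and 54.

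Optionally, add that the 90% CI of each difference from placebo will be the Newcombe (Wilson-based) interval, since no method is given for it now. Its coverage was not computed here, so this fills a gap rather than correcting a shown fault.

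The logistic regression stays as planned. The cost is a wording change and a standard software option. Intervals become wider at extreme rates: with 1 responder of 36, Wald gives −1.7% to 7.3% and Wilson 0.6% to 11.5%. In mid-range they hardly change: with 18 of 36, 36.3% to 63.7% becomes 36.8% to 63.2%.
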